Proprietary confidential information © 2023 Boehringer Ingelheim International GmbH or one or more of its affiliated companies

Section to be changed	Section 4.1.3 Method of assigning patients to treatment groups
Description of change	Removed the randomization stop for NASH patients with T2DM after reaching 20 patients in the treatment group 3
Rationale for change	See rational for change to the Clinical Trial Protocol Synopsis
Section to be changed	Table 5.2.3: 1 Safety laboratory tests
Description of change	The following was added to footnote 9 and 10: 

“Per central laboratory assay, if HCV RNA is < 15 IU/ml at screening, eligibility criteria are met”

“Per central laboratory assay, if HBV DNA is < 20 IU/ml at screening, eligibility criteria are met”

Rationale for change	Clarification for interpretation of HCV RNA and HBV DNA reflex results
Section to be changed	Section 7.2.3 Primary objective analyses
Description of change	Corrected the following wording to align with the definition of the primary endpoint (addition in bold ): “Percentage of HVPG change from baseline at Week 8...”
Rationale for change	Correction
Section to be changed	Section 7.4 Randomization
Description of change	

Confirmed that a minimum of 20 patients in treatment group 3 and a minimum of 20 patients in treatment group 4 will be required

Removed the randomization stop for NASH patients with T2DM after reaching 20 patients in the treatment group 3

Rationale for change	See rational for change to the Clinical Trial Protocol Synopsis
Section to be changed	Section 7.5 Determination of sample size
Description of change	Wording updated to confirm that a minimum of 20 patients in treatment group 3 and a minimum of 20 patients in treatment group 4 will be required
Rationale for change	See rational for change to the Clinical Trial Protocol Synopsis

## 11.5 GLOBAL AMENDMENT 5

Date of Amendment	21 Aug 2023
EudraCT No.	2021-005171-40
EU Clinical Trial No.	2023-504257-12-00
BI Trial No.	1366-0029
BI Investigational Medicinal Product	BI 685509 and empagliflozin
Title of protocol	Randomised, open-label and parallel group trial to investigate the effects of oral BI 685509 alone or in combination with empagliflozin on portal hypertension after 8 weeks treatment in patients with clinically significant portal hypertension (CSPH) in compensated cirrhosis
Global Amendment due to urgent safety reasons	
Global Amendment	x
Section to be changed	Title page
Description of change	Added EU Clinical Trial No. 2023-504257-12-00
Rationale for change	Administrative change due to transition of the trial from the EU CT Directive to the EU CT Regulation
Section to be changed	Clinical Trial Protocol Synopsis
Description of change	Changed the number of patients per treatment group from 20 to "approximately" 20
Rationale for change	To ease recruitment difficulties by permitting more than 20 patients entering the treatment groups 3 and 4 and by not requiring a minimum number of patients for treatment groups 1 and 2
Section to be changed	Section 3.1 Overall Trial Design
Description of change	

Removed the number of patients per treatment group

Confirmed that a minimum of 20 patients in treatment group 3 and a minimum of 20 patients in treatment group 4 will be required

Removed the randomization stop for NASH patients with T2DM after reaching 20 patients in the treatment group 3

Rationale for change	See rational for change to the Clinical Trial Protocol Synopsis
Section to be changed	Figure 3.1: 1 Trial Design Schematic
Description of change	

Removed the number of patients per treatment group

Confirmed a minimum of 20 patients in the treatment group 3 and 4

Removed the randomization stop for NASH patients with T2DM after reaching 20 patients in the treatment group 3

Rationale for change	See rational for change to the Clinical Trial Protocol Synopsis

Section to be changed	Section 4.1.3 Method of assigning patients to treatment groups
Description of change	Removed the randomization stop for NASH patients with T2DM after reaching 20 patients in the treatment group 3
Rationale for change	See rational for change to the Clinical Trial Protocol Synopsis
Section to be changed	Table 5.2.3: 1 Safety laboratory tests
Description of change	The following was added to footnote 9 and 10: 

“Per central laboratory assay, if HCV RNA is < 15 IU/ml at screening, eligibility criteria are met”

“Per central laboratory assay, if HBV DNA is < 20 IU/ml at screening, eligibility criteria are met”

Rationale for change	Clarification for interpretation of HCV RNA and HBV DNA reflex results
Section to be changed	Section 7.2.3 Primary objective analyses
Description of change	Corrected the following wording to align with the definition of the primary endpoint (addition in bold ): “Percentage of HVPG change from baseline at Week 8...”
Rationale for change	Correction
Section to be changed	Section 7.4 Randomization
Description of change	

Confirmed that a minimum of 20 patients in treatment group 3 and a minimum of 20 patients in treatment group 4 will be required

Removed the randomization stop for NASH patients with T2DM after reaching 20 patients in the treatment group 3

Rationale for change	See rational for change to the Clinical Trial Protocol Synopsis
Section to be changed	Section 7.5 Determination of sample size
Description of change	Wording updated to confirm that a minimum of 20 patients in treatment group 3 and a minimum of 20 patients in treatment group 4 will be required
Rationale for change	See rational for change to the Clinical Trial Protocol Synopsis
Section to be changed	not applicable
Description of change	Global Amendment 4 (CTP V5.0) was not released and not submitted as incorrect signature DMS workflow was started and the e-signature page was missing.
Rationale for change	According to the SOP BI-VQD-11930_40-106 (v14.0) a global amendment needs to be approved via a DMS e-signature workflow. By mistake the approval workflow was started in eDMS instead of the e-signature workflow and for that reason also the signature page was missing in the CTP Version 5.0

## **2. LIST OF ABBREVIATIONS**

Term	Definition / description
AE	Adverse Event
AESI	Adverse Event of Special Interest
ALQ	Above Limit of Quantification
ALT	Alanine transaminase
ANCOVA	Analysis of Covariance
AST	Aspartate transaminase
ATC	Anatomical-Therapeutic-Chemical classification
BI	Boehringer Ingelheim
BIcMQ	BI-customised MedDRA query
BLQ	Below Limit of Quantification
BMI	Body mass index
CI	Confidence Interval
CTCAE	Common Terminology Criteria for Adverse Events
CTR	Clinical Trial Report
DBL	Database Lock
DBLM	Database Lock Meeting
DILI	Drug-Induced Liver Injury
DMC	Data Monitoring Committee
DBP	Diastolic blood pressure
ECG	Electrocardiogram
EoS	End of Study (corresponds with End of Trial)
EoT	End of Treatment
FAS	Full Analysis Set
FAST TM	FibroScan-AST
Fib-4	Fibrosis-4
HVPG	Hepatic Venous Pressure Gradient
WHVP	Wedged Hepatic Venous Pressure
FHVP	Free Hepatic Venous Pressure
PFHVP	Proximal Free Hepatic Venous Pressure
ICH	International Council on Harmonisation

Term	Definition / description
IPD	Important protocol deviation
LLOQ	Lower limit of quantification
MedDRA	Medical Dictionary for Drug Regulatory Activities
PD	Protocol deviation
PK	Pharmacokinetic
PT	Preferred term
REP	Residual effect period
RPM	Report planning meeting
SBP	Systolic blood pressure
SAE	Serious Adverse Event
SD	Standard deviation
SDL	Subject data listing
SMQ	Standardised MedDRA query
SOC	System Organ Class
TOC	Table of contents
TS	Treated Set
TSAP	Trial Statistical Analysis Plan
ULN	Upper Limit of Normal
ULOQ	Upper limit of quantification

### **3. INTRODUCTION**

As per ICH E9 (1), the purpose of this document is to provide a more technical and detailed elaboration of the principal features of the analysis described in the Clinical Trial Protocol (CTP), and to include detailed procedures for executing the statistical analysis of the primary and secondary endpoints and other data.

This trial statistical analysis plan (TSAP) assumes familiarity with the CTP. In particular, the SAP is based on the planned analysis specification as written in CTP Section 7 “Statistical Methods and Determination of Sample Size”. Therefore, TSAP readers may consult the CTP for more background information on the study, e.g., on study objectives, study design and population, treatments, definition of measurements and variables, planning of sample size, and randomisation.

The statistical analyses will be performed within the validated working environment CARE, including SASTM (current Version 9.4, by [REDACTED] and several SASTM-based tools (e.g., macros for the analyses of AE data or laboratory data; Report Appendix Generator system (RAGe) for compilation/formatting of the Clinical Trial Report (CTR) appendices). Pharmacokinetic (PK) parameters will be calculated using WinNonlinTM software (version 8.1, [REDACTED]).

**4. CHANGES IN THE PLANNED ANALYSIS OF THE STUDY**

There are no changes in this TSAP compared to the statistical methods described in the CTP.

## **5. ENDPOINTS(S)**

### **5.1 PRIMARY ENDPOINT(S)**

The primary endpoint is the percentage change in HVPG from baseline (measured in mmHg) after 8 weeks of treatment.

The calculation of HVPG will be based on the measurements of wedged hepatic venous pressure (WHVP) and free hepatic venous pressure (FHVP).

The average WHVP and the average FHVP will be calculated from the triplicate measurements. Either the average FHVP or the measurement proximal free hepatic venous pressure (PFHVP) will be used as the subtrahend for the calculation of HVPG, which will be rounded to one decimal place.

Based on the judgement of the central reader, if the recorded PFHVP is considered to be more reliable than the average of the recorded triplicate FHVPs, then:

$$\text{HVPG (mmHg)} = \text{average WHVP (mmHg)} - \text{PFHVP (mmHg)};$$

if the average of the recorded triplicate FHVPs is considered to be more reliable than the recorded PFHVP, then

$$\text{HVPG (mmHg)} = \text{average WHVP (mmHg)} - \text{average FHVP (mmHg)}.$$

The quality of the HVPG will be categorized into optimal, sub-optimal and not evaluable based on the judgement of the central reader. A frequency table will be provided to summarize the quality of HVPG tracings measured at baseline and week 8.

#### **5.1.1 Key secondary endpoint(s)**

Since there are no key secondary endpoints specified in the CTP, this section is not applicable.

### **5.2 SECONDARY ENDPOINT(S)**

Following secondary endpoints will be analysed:

[figure not shown]
- Occurrence of a response, which is defined as > 10% reduction from baseline HVPG (measured in mmHg) after 8 weeks of treatment.
- Occurrence of one or more decompensation events (i.e., ascites, VH, and / or overt HE) during the 8-week treatment period.
- Occurrence of CTCAE grade 3 (or higher) hypotension or syncope based on Investigator judgement, during the 8-week treatment period
- Occurrence of discontinuation due to hypotension or syncope during the 8-week treatment period.

**Boehringer Ingelheim  
TRIAL STATISTICAL ANALYSIS PLAN  
1366-0029**

## **6. GENERAL ANALYSIS DEFINITIONS**

### **6.1 TREATMENT(S)**

For basic study information on the treatment to be administered, assignment to treatment, and selection of dose, refer to CTP Section 4.

There will be three study phases in this trial: screening, study treatment phase (with avenciguat and avenciguat + empagliflozin) and follow-up.

Table 6.1: 1 Flow chart of analysis phases

Label	Interval	Start date	End date
Screening	Screening	Date of informed consent	Date of first administration of study medication -1
avenciguat [REDACTED] avenciguat [REDACTED] + empagliflozin 10mg	On-treatment	Date of first administration of study medication	Date of last intake of study medication + X*
Follow-up*	Follow up	Date of last intake of study medication + X* + 1	Latest of (day of EOS visit, last contact date on EOS page)

\*X=1, 3 or REP (7) days for safety laboratory, and AE respectively. X for other variables are defined in [Table 6.7: 1](#). Follow-up phase might not exist, e.g., if the patient's trial termination date is within 7 days after last administration of study drug.

The purpose of the definitions above is to describe all the different study/treatment intervals, to which a patient can be assigned during the course of the trial.

For efficacy analyses of HVPG, data up REP+1 (8 days) after last treatment intake will be considered as on-treatment, because an HVPG measurement at EOT is permitted within 7 days after scheduled EOT (i.e., REP+1 day after last dose) as stated in Section 5.1.1 of the CTP.

The efficacy analyses will follow the intention-to-treat (ITT) principle in assigning patients to treatment groups, i.e., patients will be analysed in the treatment group they were assigned or randomised to.

AEs with an onset during the time of the incorrect study treatment will be listed separately.

## **6.2           IMPORTANT PROTOCOL DEVIATION**

Each protocol deviation must be assessed to determine whether it is an important Protocol Deviation (iPD). The documentation of the iPD categories and handling of iPDs in analysis is included in the DV domain specification and stored within the TMF in EDMS.

The decision about which protocol deviation (PD) could generate exclusion from analysis sets will be taken during the conduction of the trial and finalised at the last report planning meeting (RPM).

Non-important COVID-19 related PDs will only be listed.

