#### **4.1.5 Blinding and procedures for unblinding**

Although a randomization is applied to NASH patients with T2DM, the patients, investigators and sponsors will stay unblinded due to the open-label nature of this trial.

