## 5. ASSESSMENTS

### 5.1 ASSESSMENT OF EFFICACY

#### 5.1.1 Hepatic venous pressure gradient

HVPG measurement will be performed at the time points specified in the [Flow Chart](#). Sites must have access to the necessary infrastructure and equipment to measure HVPG (e.g. a hepatic haemodynamic laboratory at their site, or at a nearby institution). Site staff performing the procedure must have sufficient expertise (e.g. performing in the region of 25 or more HVPG measurements per year) with interventional skills and expertise in the reading of pressure tracings, since a local interpretation of the tracing from Visit 1c will be required for eligibility purposes (refer to [Section 3.3.2](#)).

The HVPG procedure within the trial will be conducted in a standardised fashion at all sites (for details refer to the HVPG manual in the ISF); training will be provided. Each trial site will be asked to provide acceptable sample HVPG tracing(s) prior to commencing patient recruitment if not already provided for Trial 1366-0021. Measurements of wedged hepatic venous pressure (WHVP) and free hepatic venous pressure (FHVP) will be performed in triplicate; tracings will be provided to an external Supplier and read centrally by independent expert(s) in PH; the central read will include a subjective assessment of the overall trace quality as well as a read of the relevant pressures. The independent expert(s) will be blinded to the timepoint that the trace relates to. The central read will include the traces from Visit 1c that have also been interpreted locally. The results of the central read will be transferred to the Sponsor and will be considered the official evaluation of the trial. In case of discrepancies between a local interpretation and the central evaluation (e.g. of the Visit 1c tracing), the central evaluation will remain valid.

HVPG measurements should be performed using the same hepatic vein, prior to intake of the trial medication, after an overnight fast, and ideally in the morning. If it is not possible to perform the measurement at Visit 1c in the morning an alternative time of day can be chosen; in this case, a fast of at least four hours is required. The subsequent HVPG measurement must then be performed at approximately the same time of day as the Visit 1c measurement for a single patient.

[figure not shown]

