### **7.2 PLANNED ANALYSES**

#### **7.2.1 General considerations**

[figure not shown]
The analyses will be performed based on the following analysis sets:

- **Enrolled set (ES)** – this analysis set includes all patients having signed informed consent and who were eligible for inclusion into the trial. The ES will be used for analyses of patient disposition
- **Randomised set (RS)** – this analysis set includes all enrolled patients that were entered or randomised to the trial medication. The RS will be used for demographic and baseline disease characteristics presentation
- **Treated set (TS)** – the treated set includes all patients who were enrolled or randomised to the trial medication and were treated with at least one dose. The TS will be used for all safety analyses
- **Full analysis set (FAS)** – this analysis set includes all enrolled or randomised patients who received at least one dose of trial medication and have a baseline measurement for the primary endpoint recorded. The FAS will be used for the efficacy analyses

Further analysis sets will be defined in the TSAP, if needed.

Efficacy analyses will be performed based on the planned treatment (i.e. the treatment assignment at randomisation). Safety analyses will be based on the actual treatment received at the enrolment/randomisation visit.

Unless otherwise stated, baseline is defined as the latest measurement before the first trial medication intake.

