**Hepatic injury Adjudication Committee:**

An independent AC will be used to adjudicate certain hepatic injury events for severity and causal relationship with the trial medication. Events may either be defined by abnormal laboratory values and / or relevant AEs. They will be defined in the hepatic injury AC charter. For qualifying events, relevant source documents generated from any medical evaluations of these events will be requested. Relevant source documents might include laboratory values, histological analysis, reports from ultrasound, computed tomography (CT), magnetic resonance imaging (MRI), hospital discharge letters and medical reports from other physicians.

Relevant documentation on the participating (Principal) Investigators (e.g. their curricula vitae) will be filed in the ISF. The Investigators will have access to the BI web portal Clinergize to access documents provided by the Sponsor.

BI has appointed a Clinical Trial Leader responsible for coordinating all required activities, in order to:

- manage the trial in accordance with applicable regulations and internal SOPs
- direct the clinical trial team in the preparation, conduct and reporting of the trial
- ensure appropriate training and information of Clinical Trial Managers, CRAs and Investigators of participating countries

In the participating countries the trial will be performed by the respective local or regional BI-organisation (Operating Unit) in accordance with applicable regulations and BI SOPs, or by a CRO based on a contract. The CRO will perform project management, clinical field monitoring, medical monitoring, and reporting.

Data Management and statistical evaluation will be done by BI according to BI SOPs.

Tasks and functions assigned in order to organise, manage, and evaluate the trial are defined according to BI SOPs. A list of responsible persons and relevant local information can be found in the ISF.

A central laboratory service, a central reading service for HVPG, an IRT supplier and other central services / equipment will be used / provided in this trial. Details will be provided in the respective manuals and will be available in the ISF.

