### **6.4 SUBJECT SETS ANALYSED**

The subject sets will be used as defined in the CTP, Section 7.2.1. These include the Treated set (TS) and Full analysis set (FAS).

- Screened set (SCR) – this analysis set includes all patients having signed informed consent. The SCR will be used for analyses of patient disposition.

The discussion on all exceptional cases and problems and the decisions on the allocation of patients to populations will be made at latest at DBLM.

In [Table 6.4:1](#) the subject sets which are to be used for each class of endpoint are illustrated.

Table 6.4: 1 Subject sets analysed

	Subject set		
Class of endpoint	SCR	TS	FAS
Disposition	X		
Primary endpoint			X
Secondary efficacy endpoints			X
Safety endpoints & treatment exposure		X	
Demographic/baseline endpoints		X	

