**Page 31 of 35**

**c44538732-01**

Proprietary confidential information © 2024 Boehringer Ingelheim International GmbH or one or more of its affiliated companies.

**8. TIMEPOINT OF RELEASE OF TREATMENT  
INFORMATION**

Not applicable as no blinding procedure is needed.

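### SAP 6.2 lets protocol deviations exclude patients from analysis sets, decided during an open-label trial, which conflicts with the FAS definition and the treatment-policy estimand

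*SAP*

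**What the plan says.** **Exclusions.** SAP 6.2 states: "The decision about which protocol deviation (PD) could generate exclusion from analysis sets will be taken during the conduction of the trial". The decision is finalised at the last report planning meeting. The same section says that the deviation categories and their handling in the analysis are held in a DV domain specification in the trial master file, which is not reproduced. In SAP 6.4, where exceptional cases are discussed, "the decisions on the allocation of patients to populations will be made at latest at DBLM" (the database lock meeting). SAP 7 plans a per-patient listing of important deviations that marks whether each one led to exclusion from an analysis set.

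**The efficacy set.** Protocol 7.2.1 gives the FAS definition as follows: "this analysis set includes all enrolled or randomised patients who received at least one dose of trial medication and have a baseline measurement". The measurement meant is HVPG. It sets no condition on protocol deviations. SAP 6.4 takes over the protocol's sets, and its Table 6.4:1 assigns the primary and secondary efficacy endpoints to the FAS. No per-protocol set is defined. SAP 4 declares no changes from the protocol's statistical methods.

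**The estimand.** SAP 6.3 handles every listed intercurrent event by treatment policy. SAP 7.4.1 keeps data collected after those events.

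**Who knows what.** Protocol 4.1.5: "the patients, investigators and sponsors will stay unblinded due to the open-label nature of this trial". SAP 8, on release of treatment information: "Not applicable as no blinding procedure is needed". Protocol 5.1.1: "The results of the central read will be transferred to the Sponsor and will be considered the official evaluation of the trial". Protocol 8.7: "Data Management and statistical evaluation will be done by BI according to BI SOPs".

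**The concern.** An exclusion rule that is settled while the trial runs is usually protected by the blind: those who decide do not know the treatment, so they cannot steer the comparison. Here there is no blind. All four groups receive the investigational drug, and with no placebo group the result of interest is each group's own mean change. For that quantity the protection that matters is ignorance of the patient's Week 8 HVPG, and the documents state no such protection. The central reader is blinded to the timepoint of the trace, which protects the reading but not the decision on who is analysed.

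Groups 3 and 4 are planned at a minimum of 20 patients each, and groups 1 and 2 have no stated minimum, so one or two exclusions carry weight. Protocol 3.2 also intends an indirect comparison with trial 1366-0021, and a shifted group mean would pass straight into it.

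**Working it through.** **1. The passages side by side**

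- Table 6.4:1 has three sets: SCR, TS and FAS. The FAS is the only one used for efficacy, so it is the only efficacy set on which SAP 6.2 could act.
- Protocol 7.2.1 gives the FAS two conditions, both fixed by the time of the first dose. A deviation-based removal would add a third. SAP 4 says that nothing has changed.
- Use of a restricted NO-sGC-cGMP therapy is an intercurrent event in SAP 6.3, to be handled by treatment policy. It also departs from protocol 4.2.2.1, and protocol section 8 treats departures from the protocol as deviations. The same patient could therefore be kept under SAP 6.3 and 7.4.1 and removed under SAP 6.2.
- SAP 7.4.1 also limits the analysis to on-treatment HVPG. That is a rule on when the value was measured and does not supply a deviation criterion.

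For efficacy, the SAP 6.2 clause is thus either without effect or in conflict with protocol 7.2.1 and SAP 4, 6.3, 6.4 and 7.4.1.

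**2. Reproducing the protocol's own figures**

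Inputs from protocol 7.5: SD 25%, n = 20 per group.

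Standard error = 25/√20 = 5.59 points.

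P(observed mean reduction ≥ 10%) = Φ((true reduction − 10)/5.59).

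| True reduction | Protocol Table 7.5:1 | Recomputed |
|---|---|---|
| 20% | at least 96.3% | 96.3% |
| 15% | at least 82% | 81.4% |
| 5% | at most 18.8% | 18.6% |
| 0% | at most 3.8% | 3.7% |

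The agreement is close enough to use the same model below.

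**3. Worst-case size of outcome-driven exclusion**

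The number of patients dropped is an assumption; the documents give none. If the k worst values of n are removed, the mean moves by SD × (sum of the k largest expected normal order statistics)/(n − k). For n = 20 the two largest are 1.867 and 1.408.

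- One dropped: 1.867 × 25/19 = 2.46 points.
- Two dropped: (1.867 + 1.408) × 25/18 = 4.55 points.

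A simulation of 400,000 groups of 20 normal values gave 2.47 and 4.56 points. The probability of an observed mean reduction of at least 10% became:

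| True reduction | None dropped | Worst one dropped | Worst two dropped | Two dropped regardless of outcome |
|---|---|---|---|---|
| 5% | 18.6% | 32.6% | 46.9% | 19.8% |
| 0% | 3.7% | 9.1% | 16.9% | 4.5% |

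Against the 15% observed reduction that protocol 7.5 calls a positive signal, a true 5% reduction passes with probability 3.7% with none dropped, 9.1% with the worst one dropped and 16.9% with the worst two dropped.

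The last column of the table shows that losing two patients matters little in itself. What matters is whether the choice depends on the outcome.

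**The case against.** A reader might infer that the plan lets the sponsor drop patients from the efficacy set with their outcome known. The documents do not support that.

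- **The FAS is already fixed.** SAP 6.4 adopts the protocol definition and SAP 4 declares no change. SAP 6.2 never names the FAS and says only that deviations could generate exclusion. The deadline in SAP 6.4 concerns exceptional cases and does not reopen the definitions.
- **Important deviations stay in.** Restricted therapy, changed NSBB or carvedilol treatment and early discontinuation fall under treatment policy. Where the SAP wants patients out of the FAS, it names them in advance as a supplementary analysis (SAP 7.4.4: down-titration or dose interruption).
- **Knowledge of outcome is not established.** Protocol 5.1.1 does not say when the central reads are transferred or who at the sponsor sees them. Attendance at the two meetings is not given either.
- **The rules may exist elsewhere.** The DV domain specification could fix them in advance.
- **Exclusions would be visible.** SAP 7 lists them per patient and tabulates the analysis sets by group. The trial is descriptive, without hypothesis tests.
- **The size is a constructed extreme.** It needs the worst responders also to have an excludable deviation. Both shifts are below one standard error (5.59 points).

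All of this stands, and it limits the point to a conflict in the text plus an open route. It does not remove the conflict: SAP 7 expects deviation-driven exclusions, and SAP 6.2 itself says that the decision is taken during conduct, whatever the unseen specification contains. Visibility helps a reader afterwards but does not restore the planned estimate. A shift below one standard error is still a bias in one direction.

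**Conclusion.** SAP 6.2, read with SAP 7, provides for deviation-based exclusion from analysis sets. That is inconsistent with the only efficacy set and with the treatment-policy estimand. Because the trial is open-label, the sponsor receives the central reads, and no visible passage separates the exclusion decision from Week 8 results, the inconsistency leaves an avoidable route to outcome-influenced exclusion.

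The shifts of about 2.5 and 4.6 points are upper illustrations. They rest on the protocol's SD of 25%, normal values, 20 patients with a Week 8 value, an assumed one or two exclusions, and a raw mean in place of the ANCOVA-adjusted mean. They are not a forecast, and nothing in the documents suggests an intent to exclude by outcome. The point should be corrected before database lock; it does not invalidate the design.

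**What to change.** In SAP 6.2, with a matching line in SAP 6.4, state that no protocol deviation removes a patient from the FAS. Add that any deviation-based exclusion is reported only as a supplementary analysis, in the manner of SAP 7.4.4, alongside the full FAS result. Check that the DV domain specification says the same.

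The cost is a few lines of SAP text. No new data are needed, nothing changes for patients or sites, and the SAP comes back into line with protocol 7.2.1.

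Holding the central Week 8 reads back from the sponsor is not proposed. No transfer schedule is shown that could be changed, and HVPG results are also site source data open to sponsor monitoring (protocol 8.3.1 and 8.3.2), so a hold would not reliably conceal them. Once the FAS is closed to deviations, the primary analysis does not need it.
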